- Clinical response, endoscopic healing, symptomatic remission, mucosal (endoscopic & histologic) healing, and deep symptomatic remission at Maintenance Week 44
- Corticosteroid-free remission at Maintenance Week 44
- Maintenance of clinical remission at Maintenance Week 44 in those who were in remission at Maintenance Week 0

Study Design:

[figure not shown]
Summary: This protocol includes three studies: a Phase 2b dose-finding Induction Study (8-16 weeks), a Phase 3 dose-confirming Induction Study (8-16 weeks), and a Phase 3 randomized-withdrawal Maintenance Study (up to 44 weeks) [Figure 1] characterizing the general treatment paradigm in UC. Each of the studies will utilize multi-center, randomized, double blind, placebo-controlled, and parallel-group designs to evaluate 1 or more dose(s) of TD-1473 compared to placebo in subjects with moderately-to-severely active UC.

The duration of treatment in the Phase 2b and Phase 3 Induction Studies will be 8 weeks for those who achieve clinical response, as defined by an adapted Mayo score (total Mayo score without inclusion of the Physician Global Assessment [PGA] component, using a centrally read Mayo endoscopic subscore), at Week 8. For subjects who do not achieve clinical response at Week 8, dosing will continue for an extended induction period of 8 weeks (16 weeks in total; TD-1473 subjects will receive the same dose for a total of 16 weeks and placebo subjects will receive a dose of 80 mg for the extended duration period). Subjects who achieve clinical response at either at Week 8 or Week 16 of the Induction Study will enter the Maintenance Study. Subjects who do not achieve clinical response by Week 16 will complete the study at Week 16 plus the End of Study visit.

During the Maintenance Study, subjects will be treated with either placebo or one of several TD-1473 doses for 44 weeks. Subjects who A) demonstrate persistent loss of response (no improvement at approximately 8 weeks after meeting loss of response criteria) or B) experience repeated (two) Clinical Flares during the Maintenance Study after loss of response or C) complete the Maintenance Study will exit the Maintenance Study and may be eligible for the long-term safety (LTS) Study (separate protocol, Protocol 0164).

Subjects will be required to maintain an electronic symptom diary to be completed on a daily basis. See below for details of the Induction and Maintenance Studies.

Figure 1: Protocol Schema

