* Estimated number of subjects for the re-randomized maintenance population

Phase 2b Dose-Finding Induction and Phase 3 Dose-Confirming Induction Studies

To determine initial eligibility, subjects will undergo assessments during the Screening Stage 1 period. Refer to Schedule of Study Procedures (Table 1) for a schedule of the screening requirements. Disease activity will be assessed by partial, adapted, and total Mayo scores. Subjects who meet inclusion criteria and no exclusion criteria, as described in Section 4, will undergo an endoscopic exam (i.e., sigmoidoscopy or colonoscopy) with biopsies to complete screening Stage 2.

If the subject meets eligibility criteria, including a Mayo endoscopic subscore ≥ 2 points from the Screening Stage 2 visit and an adapted Mayo score between 4 and 9 points, inclusive, on Day 1, the subject may be randomized. Randomization will be stratified by prior biologics failure status (yes or no) and corticosteroid use at enrollment (yes or no) into the Induction Study.

The Induction Studies consist of treatment for 8 weeks for those who demonstrate clinical response at Week 8 or 16 weeks for those who did not have a response. Subjects will return for safety, PK, biomarker, and disease assessments, as well as an endoscopy with biopsies according to the Schedule of Study Procedures provided in Table 1.

The Phase 2b Induction Study will enroll approximately 240 subjects, randomized 1:1:1:1 to placebo or 1 of the 3 TD-1473 doses (20 mg, 80 mg, or 200 mg). After all 240 subjects have

either completed Week 8 or been withdrawn from the Study prior to Week 8, an analysis of all efficacy and safety data up to Week 8 will be conducted (Refer to Section 8). Results from the Phase 2b dose-finding Induction Study analysis will be used to inform the dose selection for the Phase 3 dose-confirming Induction Study as well as the remainder of the Maintenance Study.

Following the 240th subject enrolled, recruitment will be placed on hold until the Phase 2b Induction study analysis is complete. A component of the analysis and interpretation is dose selection for further development. The Phase 3 Induction Study will commence after dose selection.

Extended Induction

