Subjects who do not demonstrate clinical response at Week 8 will receive an additional 8 weeks of treatment with TD-1473 staying on the same dose as the first 8 weeks, except those who had received placebo during the first 8 weeks will now receive TD-1473 at 80 mg (Figure 3). All subjects who undergo extended induction treatment will receive active drug, and thus, this portion of the Induction Study will not be placebo-controlled but blinding as to the specific dose of TD-1473 will be maintained. During this time, at the discretion of the investigator, subjects are permitted but are not required to begin corticosteroid taper. Those who demonstrate clinical response at the end of Week 16 will enter the Maintenance Study; those who do not demonstrate clinical response at the end of Week 16 will have an EOS visit and exit the study.

Maintenance Study

Subjects who are eligible (i.e., achieving clinical response by adapted Mayo score) for the Maintenance Study at Week 8 of the Induction Study will continue directly from the Induction Studies to the Maintenance study. Previously TD-1473 dosed subjects will be re-randomized to receive placebo or one of the TD-1473 doses. Subjects who achieved clinical response on placebo at Week 8 during Induction will continue on placebo in a blinded manner and will not be included in the primary efficacy analysis population of the Maintenance Study.

Subjects who are eligible (i.e., achieving clinical response by adapted Mayo score) for the Maintenance Study at Week 16 of one of the Induction Studies will continue from the Induction Studies to the Maintenance Study. Subjects who received 16 weeks of TD-1473 treatment will continue on the same study drug treatment in a blinded manner and will not be included in the primary efficacy analysis. Subjects who received 8 weeks of placebo and 8 weeks of TD-1473 80 mg will be re-randomized to placebo or one of the TD-1473 doses and contribute to the primary efficacy analysis population of the Maintenance Study.

The Maintenance Study consists of treatment for 44 weeks. During the Maintenance Study, subjects must start (or continue if they started during extended induction) tapering their corticosteroid dose using the regimen outlined in Section 6.5.3 if they entered the study on corticosteroids.

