Prior to the Phase 2b Induction Study Week 8 data analysis and subsequent dose selection, qualifying subjects from the Phase 2 Induction Study will be randomized 1:1:1:1 to placebo or 1 of the 3 TD-1473 doses (20 mg, 80 mg or 200 mg) into the Maintenance study.

After the Phase 2b Induction primary Week 8 data analysis and subsequent dose selection have been completed, subjects enrolling into the remaining of the Maintenance Study will be randomized to either placebo or one of up to two selected TD-1473 doses in a 1:1:1 ratio. Those who are still completing the Maintenance Study on a de-selected dose will remain on that dose unless there is a safety signal detected up to point of dose selection. The randomization will be stratified by clinical remission status (yes or no) (using adapted Mayo score component definition) at Maintenance Week 0 (mWeek 0) and corticosteroid use at enrollment (yes or no) into the Maintenance Study. Separate randomization schedules will be prepared for subjects who reach clinical response after receiving 8 weeks of TD-1473 and subjects who reach clinical response after receiving placebo during the first 8 weeks and then TD-1473 80 mg during extended induction.

During the Maintenance Study, subjects will return for safety, PK, biomarker, and disease assessments, as well as a final endoscopy with biopsies according to the Schedule of Study Procedures provided in [Table 2](#). Subjects who experience a clinical flare (Refer to [DEFINITION OF TERMS](#)) of their symptoms during the Maintenance Study will undergo assessment for loss of response as per [Table 3](#). Loss of response may lead to initiation of rescue medication (e.g., initiation or increase in corticosteroid dose [Refer to Section [6.5.4](#)]), which may lead to meeting the definition of treatment failure during the Maintenance Study. Subjects who complete the Maintenance Study or experience persistent loss of response or Clinical Flare twice after loss of response may enter the LTS Study (separate protocol) if they meet the applicable eligibility criteria. Subjects who do not enter into the LTS study will need to complete an End of Study visit 4 weeks after the last dose of study drug.

Refer to Section [2](#) Study Design in the main body of the protocol for further information.

Duration of Study Participation: Maximum of 68 weeks (4 weeks screening, 52/60 weeks treatment [includes 8 weeks of Extended Induction], and 4 weeks follow-up)

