Subjects who do not demonstrate clinical response at Week 8 will receive an additional 8 weeks of treatment during an extended induction period. Those that had been randomized to TD-1473 during the first 8 weeks will remain on the same dose; those who received placebo during the first 8 weeks will receive TD-1473 80 mg from Week 8 to 16. This portion of the Induction Study will not be placebo-controlled but blinding as to the specific dose of TD-1473 will be maintained. Those who demonstrate clinical response at Week 16 will enter the Maintenance Study; those who do not exit the study.

[figure not shown]
Randomization ratios and dosing regimens are described below:

a) Phase 2b Dose-Finding Induction Study

The Phase 2b-Dose Finding Induction Study (Figure 2) will enroll approximately 240 subjects, randomized 1:1:1:1 to placebo or 1 of the 3 active TD-1473 doses (20 mg,

80 mg or 200 mg). After all 240 subjects have either completed the Week 8 visit or terminated participation prior to Week 8, an analysis of all efficacy and safety data up to Week 8 will be performed (Refer to Section 8). Results from this analysis will be used to inform the dose selection for the Phase 3 dose-confirming Induction Study and the remainder of the Phase 3 Maintenance Study, which would be ongoing at that time.

[figure not shown]
Figure 2: Phase 2b Dose-Finding Induction Study

b) EXTENDED INDUCTION

Subjects who do not demonstrate clinical response at Week 8 will receive an additional 8 weeks of treatment with active drug staying on the same dose of TD-1473 as the first 8 weeks, and those who had received placebo during the first 8 weeks will now receive TD-1473 at 80 mg (Figure 3). All subjects who undergo extended induction treatment will receive active drug, and thus, this portion of the Induction Study will not be placebo-controlled but blinding as to the specific dose of TD-1473 will be maintained. During this time, at the discretion of the investigator, subjects are permitted but are not required to begin corticosteroid taper. Those who demonstrate clinical response at Week 16 will enter the Maintenance Study; those who do not demonstrate clinical response at Week 16 will have an EOS visit and exit the study.

[figure not shown]
Figure 3: Extended Induction Treatment Regimen

Phase 3 Dose-Confirming Induction Study

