The Sponsor plans to identify 1 dose for the Phase 3 dose-confirming Induction Study, guided by the results of the Phase 2b Induction Study. The Phase 3 Induction Study will not begin until an induction dose has been selected. In that study, a to-be-determined number of subjects (currently estimated as 640, but the final number will be determined after the Phase 2b Induction Study data analysis is completed) will be randomized in a 1:1 ratio to placebo or TD-1473. The Phase 3 Induction Study has the same study design as the Phase 2b Induction Study, with the exception of the number of treatment arms.

Figure 4: Phase 3 Dose-Confirming Induction Study Schema

PHASE 3 MAINTENANCE STUDY

Subjects who are considered to have achieved clinical response by adapted Mayo score (Refer to [DEFINITION OF TERMS](#)) using centrally read endoscopic subscore at either Week 8 or Week 16 during the Induction studies will continue in the Maintenance Study:

- Subjects who achieved clinical response on TD-1473 during induction at Week 8 will be re-randomized into the Maintenance Study to placebo or one of the TD-1473 doses and contribute to the primary efficacy analysis population of the Maintenance Study.
- Subjects who achieved clinical response on placebo during Induction at Week 8 will continue to receive placebo in the Maintenance Study in a blinded manner to maintain blind. However, these subjects will not be included in the primary efficacy analysis population of the Maintenance Study.
- Subjects who did not achieve clinical response by adapted Mayo score using centrally read endoscopic subscores to the first 8 weeks of induction treatment but responded at Week 16 will continue into the Maintenance Study:
 - Subjects who received 8 weeks of placebo and 8 weeks of TD-1473 80 mg will be re-randomized into the Maintenance Study to placebo or one of the TD-1473 doses and contribute to the primary efficacy analysis population of the Maintenance Study.
 - Subjects who received 16 weeks of TD-1473 during Induction will continue to receive same dose of TD-1473 in the Maintenance Study in a blinded manner to maintain blind. However, these subjects will not be included in the primary efficacy analysis population of the Maintenance Study.

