In summary, subjects who demonstrate clinical response to a total of 8 weeks of TD-1473 induction therapy, either at Week 8 or Week 16, will be re-randomized. Those who demonstrate response to placebo at Week 8 or those who demonstrate response to a total of 16 weeks of TD-1473 treatment at Week 16 will enter the Maintenance Study on the same study drug treatment as during Induction for the purpose of maintaining blinding. The Maintenance Study consists of treatment for 44 weeks. During the Maintenance Study, subjects must taper their corticosteroid dose using the regimen outlined in Section 6.5.3 if they entered the study on corticosteroids.

Before the Phase 2b Induction Week 8 primary data analysis and subsequent dose selection, responders to a total of 8 weeks of TD-1473 from the 240 subjects in Phase 2b Induction Study will be re-randomized 1:1:1:1 to placebo or 1 of the 3 active TD-1473 doses (20 mg, 80 mg or 200 mg) when they roll over into the Maintenance Study.

After the Phase 2b Induction Week 8 primary data analysis and subsequent dose selection have been completed, subjects enrolling into the Phase 3 Maintenance Study will be randomized to either placebo or 1 of the 2 selected doses of TD-1473 doses in a 1:1:1 ratio. Those who are still completing the Maintenance Study on a de-selected dose will remain on that dose unless there is a concerning safety signal detected up to point of dose selection, in which case, they will be transitioned to the closest of the doses that have been selected. The Sponsor plans to identify

2 doses for the Phase 3 dose-confirming Maintenance Study, guided by the results of the Phase 2b Induction Study.

The randomization will be stratified by clinical remission status at mWeek 0 using adapted Mayo score component definition, and corticosteroid use at enrollment into the Phase 3 Maintenance Study. In addition, randomization will also be stratified by subjects who reach clinical response after receiving 8 weeks of TD-1473 versus subjects who reach clinical response after receiving placebo during the first 8 weeks and then TD-1473 80 mg during extended induction.

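### The 80 mg switch for placebo non-responders in extended induction is not tied to dose selection, so Phase 3 subjects could newly start a de-selected dose

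*Protocol*

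**What the plan says.** The rule is stated four times in the protocol. The Synopsis, Study Design, in a paragraph about both Induction Studies, says that "placebo subjects will receive a dose of 80 mg for the extended duration period". The Synopsis subsection on Extended Induction and Section 5.2.1.1 both keep subjects on their dose, "except those who had received placebo during the first 8 weeks will now receive TD-1473 at 80 mg". Section 3.1, under Induction Studies, repeats that "those who received placebo during the first 8 weeks will receive TD-1473 80 mg from Week 8 to 16". None of the four makes the dose conditional.

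Section 3.1 then carries the design forward: "The Phase 3 Induction Study has the same study design as the Phase 2b Induction Study, with the exception of the number of treatment arms". Phase 3 opens after dose selection. Section 8.11 describes that selection: futile doses are ruled out, an Induction dose is chosen, safety is evaluated, and Maintenance is to study the Induction dose and probably a lower one. The Synopsis is looser about Maintenance: later entrants "will be randomized to either placebo or one of up to two selected TD-1473 doses in a 1:1:1 ratio".

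The explicit rule for de-selected doses is in Section 3.1: "Those who are still completing the Maintenance Study on a de-selected dose will remain on that dose unless there is a concerning safety signal". It concerns subjects already in Maintenance; if there is such a signal, they move to the nearest selected dose.

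Two other places bear on the point. Section 3.5.2 provides post-selection Induction schedules containing only the active dose(s) selected for Induction. Table 1, footnotes 1 and 3, describe the Week 8b visit as an occasion for re-randomization.

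**The concern.** Phase 3 Induction begins with knowledge of the Phase 2b result, yet the dose given to its placebo non-responders is written as if that result were not known. If 80 mg has been dropped from both Phase 3 studies, the extended-induction text still starts people on it.

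What is at stake depends on why 80 mg was dropped:

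- **200 mg alone, lower doses futile.** Placebo non-responders would begin 8 weeks on a dose just judged ineffective. Those not responding at Week 16 leave the study, and Section 3.1 describes entry to the long-term safety study only for subjects coming from Maintenance. They would leave this protocol without having received the selected dose.
- **20 mg alone, higher doses dropped for safety.** Subjects would newly start a dose set aside for safety, while the written transition protects only those already in Maintenance.
- **200 mg and 20 mg.** 80 mg was passed over in favour of doses on either side of it. The objection is much weaker here.

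**Working it through.** The plan gives no figure for this point, so there is none to reproduce. The check is a comparison of texts followed by a simple scale calculation.

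**1. Does the rule reach Phase 3?** Yes. The Synopsis paragraph covers both Induction Studies. Section 3.1 exempts only the number of treatment arms from the common design, and the placebo switch is not a treatment arm of the randomized comparison.

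**2. Can 80 mg be absent from both Phase 3 studies?** Under the planned two Maintenance doses, one of them the Induction dose (Sections 3.1 and 8.11), the possible pairs are:

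| Selected pair | 80 mg still in Phase 3? |
|---|---|
| 80 and 20 mg | yes |
| 200 and 80 mg | yes (at least in Maintenance) |
| 200 and 20 mg | no |

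So 80 mg is absent in 1 of 3 pairs. Section 8.2.3 likewise plans for a single de-selected dose. The Synopsis wording also permits one selected dose: with 20 mg alone or 200 mg alone, 80 mg is absent; with 80 mg alone, it is present.

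**3. Does other text replace the 80 mg?** The de-selected-dose rule does not, because it applies to subjects already in Maintenance. Section 3.5.2 could, if Week 8b assignment runs through the modified Induction schedules, as the Table 1 footnotes can be read to imply. But then Section 3.5.2 contradicts Sections 3.1 and 5.2.1.1, which name 80 mg outright. The visible text is inconsistent on the point, not silent.

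**4. Is Phase 2b affected?** No. Section 3.9 of the Phase 2b SAP freezes the data after the last subject in induction has reached Week 8b or mWeek 0, or has discontinued. The Phase 2b switches to 80 mg therefore come before selection.

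**5. Scale, where the condition is met.** Inputs: a planned Phase 3 placebo arm of 320 (Section 8.2.2, provisional); a Week 8 placebo response r that the documents do not state, taken as 50% to 20%. Number switched = 320 × (1 − r):

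- r = 50%: 320 × 0.50 = 160
- r = 20%: 320 × 0.80 = 256

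With an assumed 10% withdrawal before Week 8, 320 × 0.90 = 288, giving:

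- r = 50%: 288 × 0.50 = 144
- r = 20%: 288 × 0.80 = 230.4, about 230

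**6. Downstream wording.** Section 3.1 says "Subjects who received 8 weeks of placebo and 8 weeks of TD-1473 80 mg will be re-randomized into the Maintenance Study". The Synopsis, Section 3.5.2, Section 8.2 and Sections 1.2 and 1.3 of the Maintenance SAP also tie the placebo-switch group to 80 mg. Changing the Phase 3 switch dose without changing these would leave the new switchers outside the literal eligibility and stratum text.

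**The case against.** The best case for the plan has several parts.

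- **Section 3.5.2 restricts post-selection Induction schedules to selected doses.** This stands in part. It shows that the sponsor had the matter in view, and it rules out saying the protocol never addresses selected doses in Phase 3 Induction. It does not mention the switch, and the sections that do mention it say 80 mg.
- **The trigger is narrow.** This stands. A reader might count the six possible one- or two-dose selections, find 80 mg absent from three, and infer that half of all outcomes are affected. The documents do not support that reading: two of those three are single-dose outcomes outside the planned two-dose Maintenance. In the remaining one, 200/20 mg, 80 mg has not been shown futile or unsafe.
- **Safety oversight exists.** This also stands. The monitoring committee can recommend pausing or stopping (Section 6.6.3), and individual stopping rules apply (Sections 6.6.1, 7.1.4 and 7.2). They are general protections and do not choose the switch dose.
- **Relevant text may be out of sight.** Sections 3.2 and 3.3 are redacted, Figures 3 and 4 are not shown, and the Phase 3 Induction SAP is not among the documents. A qualifier there cannot be excluded.
- **A constant 80 mg may be deliberate.** It keeps the placebo-switch stratum uniform and keeps the dose blinding in extended induction meaningful. No visible text gives this reason. The benefit is also small, since extended-induction results are only summarised descriptively (Section 8.5.5).
- **Phase 3 was provisional and expected revision after Phase 2b.** True, and that makes correction easy. It does not make the written rule right.

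**Conclusion.** The point holds as a conditional and minor one. As visible, the protocol fixes 80 mg for placebo non-responders in both Induction Studies without reference to dose selection, and this fits poorly with its own provision for selected-dose schedules. Under the planned selection the mismatch arises only with 200/20 mg, where 80 mg was passed over. The more serious form, newly starting a dose dropped for futility or safety, requires selection of 20 mg or 200 mg alone.

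Where it applies, about 160 to 256 of 320 Phase 3 placebo subjects would be switched, or about 144 to 230 with 10% early withdrawal. These ranges rest on an assumed placebo response of 50% to 20% and a provisional arm size.

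A reader might infer damage to the trial's inference. The documents do not support this: the switch comes after the Week 8 endpoint, extended induction is descriptive, and Maintenance re-randomises these responders within their own stratum. Nor should anyone infer that patients were exposed in this way. Section 1 of the Maintenance SAP records early termination after lack of efficacy in Phase 2b, and the planned report covers only Phase 2b Induction and Maintenance. This is a comment on the plan as written.

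**What to change.** Make the change at or before the post-Phase 2b amendment. The Synopsis provides the opening: "Following the 240th subject enrolled, recruitment will be placed on hold until the Phase 2b Induction study analysis is complete".

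1. Keep 80 mg for Phase 2b.
2. In the Synopsis (Study Design and Extended Induction) and Sections 3.1 and 5.2.1.1, state that Phase 3 placebo non-responders receive the dose selected for Phase 3 Induction. If two Induction doses are selected, name in advance which one applies. 80 mg may stay if it is a selected dose for either Phase 3 study.
3. State that no de-selected dose is newly started.
4. Replace the fixed 80 mg with that wording in the re-randomisation and stratum text: Synopsis (Maintenance Study), Sections 3.1, 3.5.2 and 8.2, and Maintenance SAP Sections 1.2 and 1.3.

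The cost is amendment wording and a setting in the randomization and supply system before Phase 3 opens, with no added patients or procedures. There are two downsides. The placebo-switch stratum may mix 80 mg switchers from Phase 2b with Phase 3 switchers on another dose. The dose-blinding sentence also needs rewording, because with a single Phase 3 dose everyone in extended induction may be on the same one; the original Week 0 to 8 assignment stays blinded.
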